### ***10.3.2 Powered Secondary Endpoints***

#### ***Powered Secondary Endpoint 1: TLF through 1 year***

TLF at 1-year will be tested for non-inferiority. This analysis will consist of ~2600 subjects in ABSORB IV.

The hypothesis test is designed to show non-inferiority of Absorb BVS to XIENCE for the TLF at 1 year with a one-sided alpha of 0.025. The null ( $H_0$ ) and alternative ( $H_A$ ) hypotheses are:

$$H_0: TLF_{\text{Absorb}} - TLF_{\text{XIENCE}} \geq \Delta_{\text{TLF}}$$

$$H_A: TLF_{\text{Absorb}} - TLF_{\text{XIENCE}} < \Delta_{\text{TLF}}.$$

$TLF_{\text{Absorb}}$  and  $TLF_{\text{XIENCE}}$  are the 1 year TLF rates in the Absorb BVS and XIENCE arms, respectively.  $\Delta_{\text{TLF}}$  is the non-inferiority margin for this powered secondary endpoint.

The power calculation for the secondary endpoint of TLF at 1 year is based on the following assumptions:

- The true 1 year TLF rate is assumed to be 9.7% for both the Absorb BVS arm and the XIENCE arm.
- One-sided alpha: 2.5%
- Non-inferiority margin ( $\Delta_{\text{TLF}}$ ): 4.8%
- Randomization ratio (ABSORB IV): 1 (Absorb BVS arm) : 1 (XIENCE arm)
- 5% loss to follow-up at 1 year

With the effective sample size 2470 (Absorb BVS: 1235, XIENCE: 1235) at 1 year, the study has approximately 98% power to demonstrate non-inferiority of Absorb BVS to XIENCE using Farrington and Manning test.

#### ***Power Secondary Endpoint 2: Angina through 1 year***

The Angina Powered Secondary Endpoint of percentage of patients who had angina within 1 year (excluding an angina blanking period of the index hospitalization or the first 7 days post PCI, whichever occurs first) will be tested for non-inferiority with reflex testing to superiority. This analysis will consist of ~2600 subjects in ABSORB IV.

The hypothesis test is designed to show non-inferiority of Absorb BVS to XIENCE for angina within 1 year with a one-sided alpha of 0.025. The null ( $H_0$ ) and alternative ( $H_A$ ) hypotheses are:

$$H_0: ANGINA_{\text{Absorb}} - ANGINA_{\text{XIENCE}} \geq \Delta_{\text{ANGINA}}$$

**Confidential and Proprietary**

**Do not distribute or reproduce without the prior written permission of Abbott Vascular Inc.  
ABSORB III Randomized Control Trial Version 17.0 August 16, 2018.**

$H_A: \text{ANGINA}_{\text{Absorb}} - \text{ANGINA}_{\text{XIENCE}} < \Delta_{\text{ANGINA}}$ .

$\text{ANGINA}_{\text{Absorb}}$  and  $\text{ANGINA}_{\text{XIENCE}}$  are the percentage of patients with angina within 1 year in the Absorb BVS and XIENCE arms, respectively.  $\Delta_{\text{ANGINA}}$  is the non-inferiority margin for this secondary endpoint.

The power calculation for the Angina Secondary Endpoint within 1 year is based on the following assumptions:

- The true percentage of patients with angina within 1 year is assumed to be 22.6% for both the Absorb BVS arm and the XIENCE arm
- One-sided alpha: 2.5%
- Non-inferiority margin ( $\Delta_{\text{ANGINA}}$ ): 7%
- Randomization ratio (ABSORB IV): 1 (Absorb BVS arm) : 1 (XIENCE arm)
- 5% loss to follow-up at 1 year

With the effective sample size 2470 (Absorb: 1235, XIENCE: 1235) at 1 year, the study has approximately 99% power to demonstrate non-inferiority of Absorb BVS to XIENCE using Farrington and Manning test.

If the non-inferiority of Absorb BVS to XIENCE is demonstrated and the percentage is lower in Absorb BVS compared to XIENCE, a superiority test will be performed at the two sided alpha 0.05 level.

The null ( $H_0$ ) and alternative ( $H_A$ ) hypotheses are:

$H_0: \text{ANGINA}_{\text{Absorb}} - \text{ANGINA}_{\text{XIENCE}} = 0$

$H_A: \text{ANGINA}_{\text{Absorb}} - \text{ANGINA}_{\text{XIENCE}} \neq 0$

$\text{ANGINA}_{\text{Absorb}}$  and  $\text{ANGINA}_{\text{XIENCE}}$  are the percentage of patients with angina within 1 year in the Absorb BVS and XIENCE arms, respectively.

With the effective sample size 2470 at 1 year, the study has approximately 86% power to demonstrate superiority with a difference of 4.9% between the Absorb BVS arm and the XIENCE arm (e.g. 17.7% in the Absorb BVS arm vs. 22.6% in the XIENCE arm) using Pearson's Chi-square test.

The sample size calculations were performed using NCSS PASS 11 (Hintze, J., 2011, NCSS, LLC. Kaysville, Utah).

## 10.4 Statistical Analyses

For binary variables such as TLF, TLR, and clinical procedure success, counts, percentages, and 95% confidence intervals will be calculated, and p-values may be presented for hypothesis generating purposes. Pearson's Chi-squared test or Fisher's exact test will be performed when

Confidential and Proprietary

Do not distribute or reproduce without the prior written permission of Abbott Vascular Inc.  
ABSORB III Randomized Control Trial Version 17.0 August 16, 2018.

appropriate. In addition, logistic regression will be performed to determine whether the baseline characteristics exhibit any trends in predicting TLF.

For continuous variables such as age, means, standard deviations, and 95% confidence intervals for the mean will be calculated and p-values may be presented for hypothesis generating purposes. For time-to-event variables, such as time to TLF, survival curves will be constructed using Kaplan-Meier estimates, and log rank test results may be displayed. Unless specified, analyses will be performed with pooled data across all study sites.

For further details refer to the statistical analysis plan (SAP).

#### **10.4.1 Primary Endpoint Analyses**

The ABSORB IV Primary Endpoint of TLF at 30-day will be analyzed for the ITT (~2600 subjects of ABSORB IV) and the AT populations. The primary analysis will be based on the ITT population. The non-inferiority hypothesis testing will be performed using non-inferiority test by Farrington and Manning. Non-inferiority of Absorb BVS to XIENCE will be established if the p-value for the non-inferiority test is less than 0.025.

Details of the analyses for the primary endpoints can be found in the statistical analysis plan (SAP).

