### **4.5.1 Randomization**

#### **Stratified Randomization:**

Approximately 2000 subjects will be randomized 2:1 in the primary analysis (test device: Absorb BVS vs. control device: XIENCE). As diabetes and dual lesion treatment are known risks that may influence the rate of the composite endpoint (TLF), subjects will be stratified by diabetes mellitus (diabetic vs. non-diabetic) and dual vessel treatment (single target lesion vs. dual target lesion vs. one target lesion and one non-target lesion). Subjects will also be stratified by site at some pre-specified sites (expected high-enrolling sites). Other sites will be combined to ensure a sufficient number of subjects for the attainment of the desired randomization ratio. In the Imaging Cohort for both subjects receiving IVUS and those receiving the OCT, randomization (2:1) will be stratified by diabetes mellitus (diabetic vs. non-diabetic) and intended dual vessel treatment (single target lesion vs. dual target lesion vs. one target lesion and one non-target lesion). A centralized randomization service, IVRS, will be used.

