**Confidential and Proprietary**

**Do not distribute or reproduce without the prior written permission of Abbott Vascular Inc.**  
**ABSORB III Randomized Control Trial Version 17.0 August 16, 2018.**

#### **10.4.1 Primary Endpoint Analysis**

The ABSORB III primary endpoint of TLF at 1-year follow up will be analyzed for the ITT and the PTE populations. The primary analysis will be based on the ITT population. The non-inferiority hypothesis testing will be performed using a non-inferiority test statistic by Farrington and Manning. Non-inferiority of Absorb BVS to XIENCE will be established if the p-value for the non-inferiority test is less than 0.025.

In order for ABSORB III to be successful, the primary analysis with the NI test should meet the pre-specified criterion.

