##### **4.4.1 Randomization**

###### **Stratified Randomization:**

Approximately 2600 subjects will be randomized 1:1 in the ABSORB IV trial (test device: Absorb BVS vs. control device: XIENCE). Randomization will be stratified by diabetes mellitus (diabetic vs. non-diabetic) and ABSORB III-like or not. ABSORB III-like will be determined by

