**Confidential and Proprietary**

**Do not distribute or reproduce without the prior written permission of Abbott Vascular Inc.**  
**ABSORB III Randomized Control Trial Version 17.0 August 16, 2018.**

the absence of planned staged procedure, number of target lesions  $\leq 2$ , and no biomarker positive ACS or STEMI. Subjects will also be stratified by site at pre-specified expected high-enrolling sites. Other sites will be combined to ensure a sufficient number of subjects for the attainment of the desired randomization ratio. A centralized randomization service, IVRS, will be used.

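### ABSORB IV randomises within diabetes and ABSORB III-like strata, but the protocol names and powers unstratified non-inferiority tests; they stay valid and slightly conservative, and a stratified version recovers a little precision at no cost.

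*Combined protocol and SAP*

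**What the plan says.** ABSORB IV (Part 2), section 4.4.1: "Randomization will be stratified by diabetes mellitus (diabetic vs. non-diabetic) and ABSORB III-like or not". ABSORB III-like status is set by the absence of a planned staged procedure, at most two target lesions, and no biomarker-positive ACS or STEMI. The same section adds: "Subjects will also be stratified by site at pre-specified expected high-enrolling sites"; the other sites are combined.

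ABSORB IV, section 10.4.1, on 30-day TLF: "The non-inferiority hypothesis testing will be performed using non-inferiority test by Farrington and Manning". The decision rule follows: "Non-inferiority of Absorb BVS to XIENCE will be established if the p-value for the non-inferiority test is less than 0.025". Section 10.4.2 repeats the method and the rule for 1-year TLF and for angina, with a reflex superiority test for angina. Sections 10.3.1 and 10.3.2 compute power with the same method, and with Pearson's chi-square for angina superiority. None of these places mentions strata. Section 10.4 sets the default on site: "Unless specified, analyses will be performed with pooled data across all study sites". Further detail is referred to a SAP whose text is not in the document reviewed.

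ABSORB III (Part 1), section 4.5.1: "subjects will be stratified by diabetes mellitus (diabetic vs. non-diabetic) and dual vessel treatment", with dual vessel treatment at three levels, plus site at some centres. Section 10.4.1 there: "The non-inferiority hypothesis testing will be performed using a non-inferiority test statistic by Farrington and Manning".

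**The concern.** Stratified allocation forces the arms to be alike on the strata. If the strata predict the outcome, the true sampling variance of the risk difference is the within-stratum variance. An unstratified two-proportion score test still counts the variation between strata, so its standard error is somewhat too large.

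At stake is precision, and also pre-specification. If the stratified version is not named in advance, two defensible p-values exist, and a choice between them near the margin could be made after the data are seen.

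**Working it through.** **Plan's own figures.** Inputs from ABSORB IV sections 10.3.1 and 10.3.2, one-sided alpha 0.025, 1:1 allocation. For 30-day TLF the rate is 4.9% in both arms, the margin 2.9 points, with 1287 per arm. The Farrington-Manning null standard error (restricted maximum likelihood) is 0.008796 and the alternative standard error is 0.008510.

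Power = Φ[(0.029 − 1.96 × 0.008796) / 0.008510] = Φ(1.382) = 91.65%, against a stated 92%.

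The same method gives 97.9% for 1-year TLF (stated 98%) and 98.6% for angina non-inferiority (stated 99%). Angina superiority, 17.7% against 22.6% with 1235 per arm, gives 86% (stated 86%). All reproduce without strata, so the plan was powered on the unstratified tests.

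**Variance under stratification.** With stratum shares w and stratum rates p averaging P, the within-stratum share of the variance is Σw·p(1−p) / [P(1−P)]. This equals 1 − CV² × P/(1−P), where CV² is the squared coefficient of variation of the stratum rates.

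The documents give neither stratum shares nor risk ratios. Assumed: 30% diabetic, 30% not ABSORB III-like, independent factors, the same risk ratio for each.

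- Risk ratio 1.5: per factor, mean 0.7 + 0.3 × 1.5 = 1.15 and mean square 0.7 + 0.3 × 2.25 = 1.375. CV² = (1.375/1.15²)² − 1 = 0.081.
- Risk ratio 2.0: per factor, mean 1.3 and mean square 1.9. CV² = (1.9/1.3²)² − 1 = 0.264.

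| Endpoint | P | P/(1−P) | Variance fall, RR 1.5 | Variance fall, RR 2.0 |
|---|---|---|---|---|
| 30-day TLF | 4.9% | 0.0515 | 0.42% | 1.36% |
| 1-year TLF | 9.7% | 0.1074 | 0.87% | 2.84% |
| Angina | 22.6% | 0.2920 | 2.4% | 7.7% |

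For 30-day TLF this is 0.0042 × 2574 ≈ 11 to 0.0136 × 2574 ≈ 35 subject-equivalents. The standard error falls by 0.2% to 0.7%, and the 95% half-width goes from 1.668 to 1.664 or 1.657 points. Scaling both standard errors in the power formula gives 91.76% or 92.01%, a gain of 0.11 to 0.35 of a point. For 1-year TLF, power goes from 97.9% to 98.0% or 98.2%.

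**Angina superiority.** The standard error is √[(0.177 × 0.823 + 0.226 × 0.774)/1235] = 0.01611, and 0.049/0.01611 = 3.041. Power = Φ(3.041 − 1.96) = 86.0%. Dividing 3.041 by √0.976 or √0.923 gives 86.8% or 88.6%. This applies the variance ratio at 22.6% to both arms; at the average rate of 20.15% the results are 86.7% and 88.3%. At risk ratio 2.0 the highest-risk cell would have an angina rate of about 53%, so the top of the range is generous.

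**Validity.** The unstratified 30-day test was simulated at the margin under stratum-balanced allocation (200,000 replicates, same shares). One-sided type I error was 0.0245 with no stratum effect, 0.0241 at risk ratio 1.5, 0.0237 at 2.0 and 0.0214 at 3.0.

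**The case against.** The best defence is that the plan is coherent as it stands. The named test is valid, the power statements use that same test, and a slightly conservative test makes a false non-inferiority claim less likely. The gain on the primary endpoint is a fraction of a power point and rests on assumed shares and risk ratios. All of this stands, and it keeps the point small. It does not show any advantage in leaving the strata out.

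Several stronger readings are tempting, and the documents do not support them.

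- *The test is invalid.* The simulated error never exceeded 0.025.
- *The primary interval does not match the design.* Success is decided by a p-value, and no interval is the decision quantity. The 95% intervals planned for binary variables in section 10.4 would be slightly wide for the same reason.
- *The strata are ignored altogether.* The protocol text names no strata, but it refers detail to the SAP, so a stratified version there cannot be excluded. That still leaves the protocol naming and powering an unstratified test.
- *The protocol calls both ABSORB IV factors known risks for TLF.* That statement is in ABSORB III section 4.5.1, about diabetes and dual lesion treatment. ABSORB IV says nothing of the kind about ABSORB III-like status, so its prognostic strength is assumed here.
- *About 70 subjects are lost on the primary endpoint.* That figure belongs to 1-year TLF at risk ratio 2.0 (0.0284 × 2470 ≈ 70), a secondary test already powered at 98%.

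One could also say that a fix without site does not fully follow the randomisation. That is true. But cells crossed with site would be sparse at these event rates, and pooling sites is already the plan's default.

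**Conclusion.** The point holds as a modest, free improvement for ABSORB IV. As the protocol is written, the three non-inferiority tests and the angina superiority test use none of the randomisation strata. They remain valid and are slightly conservative.

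The gain is very small for the primary endpoint and small for 1-year TLF. It is most useful for angina superiority, the least-powered of the four tests. These sizes depend on the assumed 30% and 70% shares, independent factors and risk ratios of 1.5 to 2.0; weaker factors would give less.

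For ABSORB III the case for changing the primary test has passed. ABSORB IV enrolment began only after the 2000 ABSORB III primary subjects were enrolled, and a subject entered the ABSORB IV imaging sub-study on 15 February 2015. The ABSORB III 1-year window had therefore closed well before this August 2018 version, and replacing its primary test now would be post hoc.

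**What to change.** Before ABSORB IV is unblinded, state in the SAP:

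- The non-inferiority tests for 30-day TLF, 1-year TLF and angina, and their 95% confidence intervals, use a stratified score risk difference (Miettinen-Nurminen / Farrington-Manning) with Mantel-Haenszel weights over the four diabetes by ABSORB III-like strata.
- The angina superiority test is stratified the same way, for example by Cochran-Mantel-Haenszel.
- Sites are pooled, with the reason given (sparse cells).
- The unstratified tests are kept as sensitivity analyses.

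The documents do not say whether ABSORB IV results had been unblinded by this version. If they had, the stratified tests should be reported as supportive only.

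For ABSORB III, add an analysis stratified by diabetes and lesion type (2 × 3 = six strata) as supportive only.

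The cost is SAP wording and a few lines of code. No new data and no change in sample size are needed.

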#### **10.4.2 Powered Secondary Endpoint Analysis**

The ABSORB IV Secondary Endpoint of TLF at 1-year will be analyzed for the ITT (~2600 subjects of ABSORB IV) and the AT populations. The primary analysis will be based on the ITT population. The non-inferiority hypothesis testing will be performed using non-inferiority test by Farrington and Manning. Non-inferiority of Absorb BVS to XIENCE will be established if the p-value for the non-inferiority test is less than 0.025.

Analysis of the Angina Powered Secondary Endpoint of the percentage of patients with angina within 1 year will be based on the ITT population (~2600 subjects of ABSORB IV) and the AT population. The primary analysis will be based on the ITT population. The non-inferiority hypothesis testing will be performed using non-inferiority test by Farrington and Manning. Non-inferiority of Absorb BVS to XIENCE will be established if the p-value for the non-inferiority test is less than 0.025.

If the non-inferiority of Absorb BVS to XIENCE is demonstrated and the percentage is lower in Absorb BVS compared to XIENCE, a superiority test will be performed at the two-sided alpha 0.05 level.

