### **Powered Secondary Endpoint for Angina**

Angina at 1 year (exclude angina following the index procedure through discharge, not to exceed a period of 7 days) will be evaluated using the difference between the angina rates of the two treatment arms. Superiority test will be performed with a two-sided alpha of 0.05. The null ( $H_0$ ) and alternative ( $H_A$ ) hypotheses for the superiority test are:

$$H_0: \text{ANGINA}_{\text{Absorb}} - \text{ANGINA}_{\text{XIENCE}} = 0$$

$$H_A: \text{ANGINA}_{\text{Absorb}} - \text{ANGINA}_{\text{XIENCE}} \neq 0.$$

$\text{ANGINA}_{\text{Absorb}}$  and  $\text{ANGINA}_{\text{XIENCE}}$  are the 1-year angina rates in the Absorb BVS and XIENCE arms, respectively.

Using a two-sided alpha of 0.05, assuming 5% lost to follow-up at 1 year, the trial will have approximately 90% power to demonstrate superiority with a difference of 6.3% between the Absorb BVS arm and the XIENCE arm (e.g. 16.3% in the Absorb BVS arm vs. 22.6% in the XIENCE arm) using Pearson's Chi-square test.

The powered secondary endpoint of angina at 1 year will be assessed on the primary analysis group in ABSORB III, separate from the Lead-In Group and the Imaging Cohort Subjects.

The sample size calculations were performed using SAS 9.3 (SAS Institute Inc., Cary, NC).

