#### **10.4.2 Powered Secondary Endpoint Analyses**

Analysis of the Powered Secondary Endpoints for angina, for all revascularization, for ID-TVR, and for diabetic indication will include subjects from the primary analysis group. Pearson's Chi-square test will be used for superiority testing based on the ITT and PTE populations for the powered secondary endpoint for angina. Fisher's exact test will be used for superiority testing based on the ITT and PTE populations for the powered secondary endpoints for all revascularization and for ID-TVR. Analysis of the Imaging Cohort Secondary Endpoints 1 and 2 will include pooled subjects from the Imaging Cohort of ABSORB III and ABSORB Japan. Two sample t-test will be used for superiority testing based on the ITT and PTE populations.

Details of the analyses for the powered secondary endpoints can be found in the statistical analysis plan (SAP).

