#### 7.1.2 *Subject History*

Subject history will include demographics (e.g., age, gender), cardiac history including but not limited to Canadian Cardiovascular Society (CCS) and Braunwald classification of angina, history of myocardial infarction, diabetes mellitus, hypertension, hypercholesterolemia, previous CABG and PCI, and concomitant cardiovascular medications (Refer to **Appendix II** for Definitions). In addition, measurements of weight, height, and resting blood pressure will be collected.

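### ABSORB IV tests 1-year angina with no adjustment for baseline angina class, giving up some precision at no saving; the tests themselves are valid and the stated powers are correct.

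*Combined protocol and SAP*

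**What the plan says.** **ABSORB IV tests.** Section 10.4.2 (Powered Secondary Endpoint Analysis) sets the non-inferiority test for 1-year angina: "The non-inferiority hypothesis testing will be performed using non-inferiority test by Farrington and Manning". The sentence appears there first for 1-year TLF and again for angina. Superiority follows at two-sided 0.05. The test for that step is named only in section 10.3.2, as Pearson's chi-square, with "approximately 86% power to demonstrate superiority with a difference of 4.9" percentage points (17.7% against 22.6%, 1235 per arm). The primary analysis is ITT.

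**Baseline data.** Subject history in section 7.1.2 includes the "Canadian Cardiovascular Society (CCS) and Braunwald classification of angina". Randomisation (section 4.4.1) is stratified by diabetes, by ABSORB III-like status and by site at some sites. ABSORB III-like status reflects biomarker-positive ACS or STEMI, but angina class is not a stratum. The only covariate model in section 10.4 is a logistic regression for predictors of TLF.

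**ABSORB III.** Its section 10.4.2 reads: "Pearson's Chi-square test will be used for superiority testing based on the ITT and PTE populations for the powered secondary endpoint for angina". Section 10.3.2 gives "approximately 90% power to demonstrate superiority with a difference of 6.3% between the Absorb BVS arm and the XIENCE arm" ("16.3% in the Absorb BVS arm vs. 22.6% in the XIENCE arm"). Baseline CCS and Braunwald class are collected there too.

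Both parts refer to a separate SAP for detail; its text is not in the documents supplied.

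**The concern.** ABSORB IV admits patients with silent ischemia, stable angina, unstable angina, NSTEMI and recent STEMI. Its angina endpoint (section 5.2) is any angina or angina-equivalent symptom found at interview and adjudicated; it is not limited to new or worsened symptoms. Symptom class before the procedure is therefore a plausible predictor of angina in the following year. A crude comparison leaves the variation due to that predictor in the error term.

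Angina superiority has the lowest stated power of the ABSORB IV tests: 86%, against 92% (30-day TLF), 98% (1-year TLF) and 99% (angina non-inferiority). It therefore has the least precision to spare.

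**Working it through.** **1. Reproduce the stated superiority power (ABSORB IV, section 10.3.2).** Inputs: 22.6% and 17.7%, 1235 per arm, two-sided alpha 0.05, pooled rate 20.15%.

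- Null SE = √(2 × 0.2015 × 0.7985 / 1235) = 0.01614
- Alternative SE = √[(0.226 × 0.774 + 0.177 × 0.823) / 1235] = 0.01611
- Power = Φ[(0.049 − 1.96 × 0.01614) / 0.01611] = Φ(1.078) = 85.9%. The plan states about 86%.

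**2. Reproduce the stated non-inferiority power.** Inputs: 22.6% in both arms, margin 7 points, one-sided 0.025.

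- SE = √(2 × 0.226 × 0.774 / 1235) = 0.01683
- Power = Φ(0.07 / 0.01683 − 1.96) = Φ(2.20) = 98.6%. The restricted-likelihood Farrington-Manning calculation also gives 98.6%. The plan states about 99%.

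**3. Effect of adjustment.** If baseline angina explains a share R² of the outcome variance, the variance of the adjusted risk difference is about (1 − R²) times the crude variance. Both SEs are multiplied by √(1 − R²), which is equivalent to a sample of n/(1 − R²). The documents give no R², so the range is an assumption.

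| Assumed R² | SE multiplier | Superiority power | Non-inferiority power | Equivalent N |
|---|---|---|---|---|
| 0 | 1.000 | 85.9% | 98.6% | 2470 |
| 2% | 0.990 | 86.6% | 98.7% | 2520 |
| 5% | 0.975 | 87.6% | 98.9% | 2600 |
| 10% | 0.949 | 89.3% | 99.2% | 2744 |
| 15% | 0.922 | 90.9% | 99.5% | 2906 |

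At 15%, for example, superiority power is Φ[(0.049 − 1.96 × 0.01488) / 0.01485] = Φ(1.335) = 90.9%.

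**4. Which R² is plausible?** For one yes/no baseline angina variable, with 50% to 90% of subjects symptomatic and an odds ratio of 1.5 to 4 (all assumed), R² runs from about 0.002 to 0.066 and superiority power from 86.0% to 88.2%. A multi-level variable could explain more. A split of half the subjects at 35% risk and half at 10% gives R² = 0.25 × 0.25² / (0.225 × 0.775) = 9.0%.

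**5. Is chance imbalance a further loss?** Take that same split with 1235 per arm.

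- SE of the between-arm difference in the share at high risk: √(2 × 0.25 / 1235) = 2.01 points.
- Resulting shift in the angina difference: 2.01 × 0.25 = 0.50 point.
- Crude SE of the angina difference: √(2 × 0.225 × 0.775 / 1235) = 1.68 points.
- Share of variance: 0.503² / 1.680² = 9.0%, which equals R².

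The imbalance is already inside the crude standard error, so it must not be counted again.

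**6. ABSORB III for comparison.** With 16.3% against 22.6% and 1267/633 subjects, crude power is 90.8% (stated about 90%). It would be 92.1% at R² = 5% and 94.5% at 15%.

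**The case against.** **The plan contains no error.** This stands. The crude tests are valid, the stated powers are right, and the same protocol accepts 80% power for ABSORB III ID-TVR. A reader might infer that the angina tests are biased, or the trial underpowered, because baseline angina is ignored. The documents support neither.

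**The size is assumed.** This also stands. Nothing in the documents links baseline to 1-year angina, and with a simple coding the gain could be close to nothing. ABSORB IV also requires silent-ischemia subjects to have an angina history within the past year, which narrows the spread. It does not equalise current class.

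**ABSORB III should not be treated alike.** This stands. A reader might extend the point to its angina test because the same baseline classes are collected. There, however, angina is an adverse event (section 5.2), and section 8.3.1 records only new or worsened conditions, so the outcome is already referenced to baseline. Timing also counts against a change. ABSORB IV enrolment began only after the 2000 primary ABSORB III subjects were in, and an ABSORB IV sub-study subject was enrolled on February 15, 2015 (ABSORB IV section 12.1.5). The ABSORB III 1-year window therefore closed by about March 2016, and this version is dated August 16, 2018.

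**An adjusted model adds choices.** This is true unless the model is fully written out. CCS covers stable angina and Braunwald unstable angina, so they need one combined coding. Baseline questionnaires may be completed after the procedure from recall (section 7.1.3 in both parts), which argues against SAQ-7 as a primary covariate.

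**The SAP may already contain an adjusted analysis.** That cannot be excluded. The protocol nevertheless makes the crude non-inferiority p-value the decision rule.

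**Conclusion.** The point holds for ABSORB IV as an available gain in efficiency. A baseline variable that plausibly predicts the endpoint is collected, is not a stratum and is not used. Adjustment would raise superiority power from 85.9% to between 86% and 91% if R² lies between 0 and 15%; it would raise non-inferiority power by about 1 point at most (98.6% to 99.5%). These figures rest on the plan's own event rates, on an R² that the documents do not supply, and on the large-sample result that a standardised risk difference adjusted for a prognostic baseline variable is not expected to lose precision.

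A reader might infer a second harm, an uncorrected bias from chance imbalance in baseline angina. The documents do not support that: under randomisation the imbalance is part of the crude standard error, and it is the same R² effect.

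**What to change.** First establish whether the ABSORB IV 1-year angina data are still blinded; the documents do not say.

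**If blinded**, pre-specify in ABSORB IV section 10.4.2 and in the SAP:

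- Primary estimate: a standardised (marginal) risk difference from a logistic model, with a delta-method or bootstrap standard error.
- Covariates: treatment; one categorical baseline presentation variable (silent ischemia, CCS class, Braunwald class or MI presentation, with a "missing" category so that no ITT subject is dropped for a missing covariate); and the strata diabetes and ABSORB III-like. The SAP should also state how the site strata are handled.
- Tests: the 7-point margin, then superiority, both on this estimate.
- Farrington-Manning and Pearson's chi-square as sensitivity analyses.
- SAQ-7 left out of the primary model.

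**If unblinded**, keep the crude tests as primary and report the adjusted risk difference as supportive. Do the same for ABSORB III in any case.

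The cost is SAP wording and modest programming. The endpoint, the risk-difference scale, the margin and the sample size do not change.
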